6.4. Data Review Committee

A Data and Safety Review Committee (DRC) will be established to review safety data on a regular basis to ensure safety of all subjects enrolled.

A DRC meeting is to be held at regular intervals to evaluate the safety of this study and other ongoing pediatric studies of ceftaroline fosamil. The role of the DRC members is to evaluate the safety of the pediatric studies on an ongoing basis in order to determine whether any undue safety concerns are observed, and thus whether the studies should be allowed to continue enrollment.

A detailed DRC charter will be prepared by the Investigator and agreed to by all DRC members before initiation of enrollment in this study. This charter will document the timing, membership, analysis content, and review procedures for each DRC meeting. Safety information will be prepared in advance of each DRC meeting. Safety analyses will include, at a minimum, summaries of study disposition and all SAEs, deaths, and discontinuations due to AEs, PCS laboratory results, and individual subject listings of selected safety data.

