7.10. Stopping Rules

The incidence or severity of AEs indicates a potential health hazard to subjects. The study will be stopped if treatment failures occur in two patients or severe adverse events that are due to ceftaroline in the opinion of the PI occur in two patients.

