10.2. Causality and Severity Assessments

The causality assessment must be recorded on the appropriate AE CRF. Causal relationship must be assessed by answering the following question:

Is there a reasonable possibility the study drug caused the event?

Yes: There is evidence to suggest a causal relationship between the study drug and AE, ie.:

- There is a reasonable temporal relationship between the study drug and the event, and
- The event is unlikely to be attributed to underlying/concurrent disease, other drugs, or other factors, and/or
- Positive de-challenge and/or re-challenge exist

No: There is no evidence to suggest a causal relationship between the study drug and AE, ie.:

- There is no reasonable temporal relationship between the study drug and the event, or
- The subject did not take the study drug, or

- The event is likely to be attributed to underlying/concurrent disease, other drugs, or other factors, or
- The event is commonly occurring in the (study) population independent of drug exposure

The Investigator must provide an assessment of the severity of each AE by recording a severity rating on the appropriate AE screen(s) of the subject's eCRF. *Severity*, which is a description of the intensity of manifestation of the AE, is distinct from *seriousness*, which implies a subject outcome or AE-required treatment measure associated with a threat to life or functionality (Section 11.1.2). Severity will be assessed according to the following scale.

Mild:	Minor awareness of signs or symptoms that are easily tolerated without specific medical intervention.
Moderate:	Discomfort that interferes with usual activities and may require minimal intervention.
Severe:	Significant signs or symptoms that are incapacitating with an inability to work or perform routine activities and/or that require medical intervention.

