10.4. Follow Up of Serious Adverse Events

When additional relevant information becomes available, the investigator will record follow-up information according to the same process used for reporting the initial event as described above. The investigator will follow all SAEs until resolution, stabilization, or the event is otherwise explained. DRC will follow all SAEs until resolution, stabilization, until otherwise explained, or until the last patient completes the final follow-up, whichever occurs first.

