10.5. Collecting and Reporting Adverse Events and Serious Adverse Events

Research related AEs and SAEs are collected from the signing of the informed consent form (ICF) (and assent form, if applicable) until EOT. At Month 12 follow up problems such as pathologic fractures and growth disturbances will be evaluated. The investigational site personnel are to follow unresolved AEs and SAEs at EOT until resolution or stabilization.

At each visit, subjects and/or their parent(s) (or other legally acceptable representative[s]) are to be queried regarding any new or ongoing AEs/SAEs that have occurred since the previous visit. Each, as appropriate, will be asked to volunteer information with a non-leading question such as, for the subjects, "How have you felt since your last visit?" Study center personnel will then record all pertinent information on the appropriate screens of the subject's eCRF.

All research related AEs/SAEs reported by the subject or subject's parent(s) (or legally acceptable representative[s]) or observed or otherwise identified by the Investigator (or other study site personnel) at a defined study visit or during any communication with the subject (or subject's representative[s]) occurring outside a defined study visit must be documented.

All research related AEs must be recorded on the appropriate CRF, whether or not they are considered causally related to the study drug.

For every AE, the Investigator must:

- Provide an assessment of the severity, causal relationship to the study drug), and seriousness of the event (ie, SAE).
- Document all actions taken with regard to the study drug.
- Detail any other treatment measures taken for the AE.

Within 24 business hours of learning of any AE that meets one of the criteria for an SAE, the study center personnel must report the event to Allergan on an SAE/AESI form (Global Patient Safety & Epidemiology Form) and to the FDA and IRB per regulation/local IRB policy.

If, during follow-up, any nonserious AE worsens and eventually meets the criteria for an SAE, that AE should be recorded as a new SAE.

The PI will transmit the SAE/AESI Form to the email and fax number indicated on the most current version of the form. Even if an initial report is made by telephone, an SAE/AESI form completed with all available details must still be emailed/faxed within 24 business hours of knowledge of the event at the study center.

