10.9. Laboratory Assessments

Blood samples for clinical laboratory tests and urine samples for pregnancy tests (females who have reached menarche only) will be collected at baseline and throughout the study according to the Schedule of Assessments and Procedures (Table 2-1) and Section 10.0. If a subject's estimated CrCl (as calculated using the updated Schwartz "bedside" formula; Schwartz et al, 2009) decreases to < 50 mL/min during the treatment period, the DRC should be contacted. If a subject's hemoglobin or hematocrit decreases significantly (Investigator's judgment) during IV study drug therapy, an evaluation for hemolytic anemia will be conducted per standard of care.

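### A first ceftaroline-related death or life-threatening event does not by itself meet the two-patient toxicity rule, and the protocol states no unscheduled DRC review or enrollment hold after one

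*Combined protocol and SAP*

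**What the plan says.** Section 7.10 (Stopping Rules) contains three elements. It opens by saying that how often AEs occur, or how severe they are, signals a possible hazard to subjects; that sentence attaches no threshold and no action. It then stops the study for treatment failure in two patients, or when "severe adverse events that are due to ceftaroline in the opinion of the PI occur in two patients". Death and life-threatening events have no separate provision.

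The DRC appears in three places:

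- Section 6.4: "A DRC meeting is to be held at regular intervals to evaluate the safety of this study". The interval is not given. The committee is to "evaluate the safety of the pediatric studies on an ongoing basis" and so determine whether enrollment should continue. Details go to a charter to be agreed before enrollment starts: "This charter will document the timing, membership, analysis content, and review procedures for each DRC meeting".
- Section 10.4: "DRC will follow all SAEs until resolution, stabilization, until otherwise explained", or until the last patient's final follow-up. No time limit is set for the committee's first look.
- Section 10.9: if estimated CrCl falls below 50 mL/min "during the treatment period, the DRC should be contacted". This is the only event for which the protocol requires DRC contact.

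For SAEs, Section 10.5 says that within 24 business hours "the study center personnel must report the event to Allergan on an SAE/AESI form", and to FDA and the IRB. It does not name the DRC. Section 10.7 adds written IND safety reports to FDA. Section 7.7.1 lists findings that take an individual child off study. Section 12.7 has a second study halt, also at two subjects, but for lack of improvement.

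**The concern.** Safety at the end of IV therapy is the primary objective, the children may be as young as 1 year, and the DRC is the body charged with judging whether enrollment should go on. A related death or life-threatening event is the one that most needs that judgment before the next child is dosed. As written, the mandatory stop does not act on the first such event unless another child has already had a severe related AE. The protocol states no other step that brings the event to the DRC between meetings or pauses enrollment meanwhile. It does require DRC contact for a fall in creatinine clearance, so event-driven contact was considered for a lesser event.

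A smaller point is that Section 7.10 counts severe events, while Section 10.2 separates severity (intensity) from seriousness. Whether a life-threatening event enters the count therefore depends on its severity grade, though most such events would be graded severe.

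**Working it through.** **The plan's own figures.** The stopping rule has no stated operating characteristics to reproduce. The only computed figure is the sample size in Section 6.2, and it reproduces: the smallest exact single-stage design for 0.50 against 0.80 is n = 18 with at least 13 successes (type 1 error 0.0481, power 0.867). It enters below only as the cap on enrollment.

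**Step 1: what follows a first related death or life-threatening event.**

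| Section | What it provides | DRC review or hold at the first event? |
|---|---|---|
| 7.10, first sentence | General remark on AEs | No action stated |
| 7.10, toxicity rule | Stop at two patients | No; the count is one |
| 6.4 | Meetings at unstated regular intervals; ongoing evaluation | No event trigger; charter not available |
| 10.4 | DRC follows SAEs | No deadline, no link to enrollment |
| 10.5, 10.7 | Reports to manufacturer, FDA, IRB | DRC not named, no hold |
| 10.9 | DRC contact | CrCl below 50 mL/min only |
| 7.7.1 | Individual withdrawal | Affects that child only |
| 12.7 | Halt at two non-improving subjects | Efficacy only |

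**Step 2: illustration of the consequence.** Inputs: 6 subjects per year (Section 1), so 6/12 = 0.5 per month, and 18 subjects (Section 6.2). Assumptions: Poisson accrual that does not change after the event, an event at a random point between meetings, and meeting intervals T of 3, 6 or 12 months. With m = 0.5 × T, the chance of at least one new child before the next scheduled meeting is

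P = 1 − (1 − e^(−m))/m.

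If the event is equally likely in any of the 18 children, no child remains to be enrolled when it falls in the 18th, so P is multiplied by 17/18. The last column averages min(N, 18 − k), where N is the number accrued before the meeting and k the child with the event.

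| T (months) | m | P, enrollment open | P × 17/18 | Mean new children dosed |
|---|---|---|---|---|
| 3 | 1.5 | 0.482 | 0.455 | 0.69 |
| 6 | 3 | 0.683 | 0.645 | 1.33 |
| 12 | 6 | 0.834 | 0.787 | 2.50 |

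**Step 3: if the DRC reviews sooner, but without a hold.** For a fixed delay of d days with enrollment open, m = 6 × d/365.25 and P = 1 − e^(−m).

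| d (days) | m | P |
|---|---|---|
| 7 | 0.115 | 0.109 |
| 14 | 0.230 | 0.205 |
| 28 | 0.460 | 0.369 |

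With a hold until the DRC decides, P is zero by construction.

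**Step 4: how often the two-patient rule stays silent.** The documents give no event rate. At an assumed rate p per child, the chance of exactly one event in 18 is 18p(1 − p)^17. For p = 1%, 2% and 5% this is 0.152, 0.255 and 0.376. At 5%, at least one event occurs in 0.603 of such trials, and the rule acts in 0.226.

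**The case against.** The strongest reply has four parts.

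First, the opening sentence of Section 7.10 reads like a general stopping ground that has lost its lead-in, and a single related death is the plainest case of severity indicating a hazard. That is a plausible account of the intent, but the sentence as it stands tells nobody to do anything.

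Second, the charter is the natural home for ad hoc review, and it must be agreed before enrollment. This stands as a limit: the finding concerns the protocol only. A reader might infer that no such provision exists anywhere; the documents do not support that.

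Third, the DRC evaluates safety continuously and follows every SAE, so it would probably hear of a death before its next meeting. That is reasonable, and it is why the shorter delays in Step 3 belong beside the meeting-interval figures. Neither duty sets a time for review or pauses enrollment.

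Fourth, the likelihood of harm is lowered in several ways. Three pediatric trials supply q8h safety data, and Section 4.3 describes pediatric approval for pneumonia and skin infection (Section 8.1 says otherwise). Sicker children are excluded, two children above 5 years go first, children under 2 years receive a lower dose, and affected children leave the study under Section 7.7.1. Reports go to the manufacturer, FDA and IRB. Nothing prevents the sponsor-investigator from pausing earlier, and nothing obliges further dosing. All of this stands. It makes the event less likely, or a discretionary pause more likely, but does not specify the response.

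A reader might also take the percentages in Step 2 as the risk run by this trial. They are not: they apply only once the event has happened.

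**Conclusion.** The point holds as a gap in the protocol's stated rules. The only actionable toxicity stop needs two patients, it makes no exception for death or a life-threatening event, and no protocol section states an unscheduled DRC review or an enrollment hold after a first one. This should be corrected, because safety is the primary objective and the remedy is small.

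Conditional on such an event, the chance of dosing at least one more child before the DRC acts ranges from about 11% (review in one week, no hold) to 79% (annual meetings, cap of 18 applied). Where it falls depends almost entirely on the assumed review time, which the documents do not give, and on unchanged accrual.

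A reader might go further and conclude that the trial lacks safety oversight or that the study should end at one event. The documents support neither: the DRC, regulatory reporting and individual withdrawal rules are in place, and what is missing is the immediate trigger. Confidence is medium because the charter is unseen.

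**What to change.** Keep the two-patient rule and make three edits:

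1. Repair the first sentence of Section 7.10 so that it carries an action.
2. Add to Sections 7.10 and 6.4: any death or life-threatening event (the Section 10.3 criterion) for which the Section 10.2 question, "Is there a reasonable possibility the study drug caused the event", is answered Yes is sent promptly to the existing DRC for unscheduled review, and no new child is enrolled until its decision is recorded.
3. State that deaths and life-threatening events judged unrelated also go promptly to the DRC, without an automatic hold.

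If the charter already provides this, a cross-reference replaces edits 2 and 3.

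The cost is a few sentences, possibly one extra DRC meeting, and a short pause. The causality and seriousness assessments are already collected for every AE. At 6 subjects a year, an assumed pause of 2 to 4 weeks defers 6 × 14/365.25 = 0.23 to 6 × 28/365.25 = 0.46 of a child.

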8. STUDY DRUGS

8.1. Ceftaroline Fosamil Intravenous Study Drug

Ceftaroline fosamil for injection, 400 or 600 mg per vial, is supplied as a sterile pale yellowish-white to light yellow crystalline powder in a single-dose, clear glass 20-mL vial. The excipient L-arginine is added as an alkalizing agent to maintain the pH of the constituted solution between 4.8 and 6.5.

Ceftaroline fosamil is approved in the United States for use in adults with ABSSSI or CABP. Ceftaroline fosamil is limited in pediatric subjects to investigational use only. Refer to the current ceftaroline fosamil IB (Ceftaroline fosamil, 2011) for additional information.

Dosing Information: IV ceftaroline fosamil **15 mg/kg** (or 600 mg if > 40 kg) infused over 120 (\pm 10) minutes q8h (\pm 1 hour) for children **2 years of age – 17 years** of age (inclusive).

IV ceftaroline fosamil **10 mg/kg** infused over 120 (\pm 10) minutes q 8h (\pm 1 hour) for children from **1 year of age to < 2 years** (inclusive).

8.2. Directions for Use

Vials of ceftaroline fosamil are constituted with 20.0 mL of Sterile Water for Injection; the amount of solution containing the appropriate dose is further diluted in sterile normal saline before infusion.

8.3. Storage

Vials containing unconstituted ceftaroline fosamil are stored according to labeled requirements.

8.4. Criteria for Switching to Oral Drug

A switch to PO drug (see Section 9.2.2) is allowed on or after EOIV assessments are completed and if all of the following criteria are met:

- Received at least 48 hours of IV study drug.

- Clinical signs and symptoms have been assessed.
- Ability to maintain oral intake.
- Afebrile (temperature $\leq 38.0^{\circ}\text{C}$) for at least 48 hours.
- Blood cultures are negative for 48 hours.
- CRP decreased compared with baseline value.
- Absence of new or improvement in at least 1 of the following signs and symptoms and worsening of none:
 - Extremity movement or pain.
 - Able to ambulate either unaided or with a walker or crutches.

Subjects that require IV treatment after switching to Oral drug will be discontinued from the study.

8.4.1. Oral Drug Options

The appropriate PO drug may depend on the pathogen, the options include the following:

- Preferred oral switch for subjects with infections due to methicillin-susceptible *S. aureus*, Group A streptococcus or *K. kingae*-cephalexin 75-100 mg/kg/day in three divided doses.
- Alternative PO option for subjects with proven MRSA infections due to clindamycin-susceptible is clindamycin 13 mg/kg/dose q8h. Clindamycin is also the oral agent typically selected to complete treatment when no organism is isolated.
- Linezolid is an option for completing therapy for a clindamycin resistant MRSA isolate or for patients who cannot tolerate clindamycin. Linezolid dosing is 10 mg/kg/dose q 8 hours for children ≤ 12 year old and 600 mg q 12 hours for children > 12 years old.

Dosing adjustments are discussed in Section 9.3. Consult the package inserts, labels, and local dosing guidelines regarding preparation, storage, administration, maximum doses, contraindications, warnings, precautions, and AEs reported with the use of the PO study drugs.

8.5. Dose Adjustments

Subjects with moderately (CrCl 30 mL/min to ≤ 50 mL/min) or severely (CrCl < 30 mL/min) impaired renal function (calculated using the appropriate updated Schwartz “bedside” formula; Schwartz et al, 2009) will not be enrolled in this study; thus no ceftaroline fosamil dose adjustments are expected to be required for renal impairment. However, if the subject’s estimated CrCl decreases to < 50 mL/min during the treatment period, the patient will be discontinued from the study.

8.6. Adjunctive Surgical Procedures

Details of adjunctive surgical procedure(s) related to hematogenous SA osteomyelitis that are performed for any subject in this study will be collected and documented.

8.7.Treatment Compliance

Treatment compliance will be documented in the eCRF by recording the date, time, and whether or not each IV dose study drug was completely infused and, if applicable, whether or not each intended dose of PO drug was taken.

8.8.Accountability Procedures

It is the responsibility of the Pharmacist or designee to ensure that current records of study drug inventory and accountability are maintained. Records must be readily available for inspection.

Upon receipt of study therapy drugs, the Pharmacist or designee will acknowledge receipt, visually inspect the shipment, verify the number of vials shipped are received, and document the condition of the drugs received.

All study drugs provided by Allergan should be retained at the site until otherwise instructed in writing by Allegan. Upon completion of the study all used (vials), unused, and partially used IV study drugs will be shipped to a site designated by Allergan. Refer to the Pharmacy instructions or package insert for additional information.

9. STUDY ASSESSMENTS AND PROCEDURES

The Schedule of Assessments and Procedures is located in Table 2.1. Unless otherwise noted, the assessments and procedures should be conducted in person by the Investigator or designee.

Any protocol-required evaluations (eg, laboratory tests and) already done locally on the corresponding study day, including baseline, as part of the subject's regular medical care can be recorded on the eCRFs and do not have to be repeated for purposes of this study.

9.1.Baseline

Baseline procedures must be completed within 24 hours before the start of the first dose of IV study drug. Potential subjects who do not meet entrance criteria may, as appropriate, repeat baseline evaluations at a later time for possible enrollment into the study.

- Obtain informed consent in writing from parent(s) or legally acceptable representative(s) and assent from subject (as applicable) before initiating any study assessment or procedure.
- Collect demographic information including age, gender, race and ethnicity.
- Clinical Assessments (assessments will be performed for research unless they are already being performed per standard of care; exceptions are indicated):
 - Obtain a complete medical and surgical history, including history of surgical procedures for complications of hematogenous SA osteomyelitis (eg, drainage of the bone) and all active conditions and all conditions diagnosed within the previous 5 years (from the following categories: allergic; cardiovascular; dermatological; gastrointestinal; genital and reproductive; head, eyes, ears, nose, and throat; hematology; hepatic; immunological; metabolic and endocrine; musculoskeletal;

neurologic; psychiatric; renal; and respiratory).

- o Record prior medications (Section 8.3) taken or received within 14 days before the first dose of study drug. For children who are being breast fed, record all medications taken by the lactating mother during the 3 days before the first dose of IV study drug. In addition, record history of pneumococcal vaccinations.
- o Record standard of care radiology results.
- o Record the findings of a complete physical examination including physical findings of hematogenous SA osteomyelitis (eg, warmth, tenderness, swelling, erythema, and movement of the infected extremity). Involved extremity will be assessed as at enrollment, if possible. Most of the subjects are expected to have surgical incision and drainage procedures and thus assessing the extremity for swelling, erythema, warmth and tenderness may not be possible because of drains in place and large surgical dressings that cannot be removed.
- o Record height and weight.
- o Record vital signs: resting pulse, blood pressure, and respiratory rate; and highest daily temperature (Tmax) measured.
- o Identify, assess, and record any AEs and SAEs starting from the time that informed consent is obtained.
- o Record adjunctive therapeutic procedures (eg, surgeries).

Laboratory Assessments (assessments will be performed for research unless they are already being performed per standard of care; exceptions are indicated)

- o Any protocol-required eligibility laboratory evaluations already done locally as part of the subject's regular medical care within 24 hours before the start of the first dose of IV study drug do not have to be repeated for purposes of this study.
- o Collect complete blood count (CBC) with differential and CRP, ESR, BUN, and Creatinine lab results.
- o Blood cultures per standard of care.
- o Obtain blood samples for Alkaline Phosphatase, Bilirubin, AST and ALT.
- o Obtain blood sample for Direct Coombs test.
- o Obtain urine sample for pregnancy test (for a female who has reached menarche); ensure that the test is negative before enrollment.
- o Estimate CrCl using the updated Schwartz "bedside" formula (Schwartz et al, 2009):
$$\text{CrCl (mL/min/1.73m}^2\text{)} = \frac{0.413 \times \text{height (length) (cm)}}{\text{serum creatinine (mg/dL)}}$$
- o Collect purulent material from bone only if a procedure is performed for standard of care.

- Enroll subject after verifying that the subject meets all study inclusion and no exclusion criteria. There

should be no medically inappropriate delay in enrollment and subsequent administration of IV study drug.

9.2. Study Day 1

- Study Drug Administration:

IV ceftaroline fosamil **15 mg/kg** (or 600 mg if > 40 kg) infused over 120 (\pm 10) minutes q8h (\pm 1 hour) for children **2 years of age – 17 years** of age (inclusive).

IV ceftaroline fosamil **10 mg/kg** infused over 120 (\pm 10) minutes q 8h (\pm 1 hour) for children from **1 year of age to < 2 years** (inclusive).

The following Clinical and Laboratory Assessments for Study Day 1 do not need to be repeated if dosing of study medicine is done on the same day as the baseline visit:

- Clinical Assessments - after at least 1 dose of IV study drug (assessments will be performed for research unless they are already being performed per standard of care; exceptions are indicated):
 - o Record concomitant medications (Section 8.3). For subjects who are being breast fed, record all medications taken by the lactating mother.
 - o Record resting vital signs (pulse, blood pressure, and respiratory rate), and highest postdose temperature measured.
 - o Record adjunctive therapeutic procedures (eg, surgeries).
 - o Record standard of care radiology results.
 - o Evaluate and record physical findings of hematogenous SA osteomyelitis (eg, warmth, tenderness, swelling, erythema, and movement of the infected extremity). Most of the subjects are expected to have surgical incision and drainage procedures and thus assessing the extremity for swelling, erythema, warmth and tenderness may not be possible because of drains in place and large surgical dressings that cannot be removed. The degree of the subject's ability to ambulate will be assessed if the osteomyelitis is in the lower extremity-i.e. walks unaided, able to bear weight, can walk aid using a walker, etc. The use of upper and lower extremities will be assessed in terms of movement and range of motion.
 - o Identify, assess, and record any new or ongoing AEs or SAEs
- Laboratory Assessments - after at least 1 dose of IV study drug (assessments will be performed for research unless they are already being performed per standard of care; exceptions are indicated)
 - o If clinically indicated, calculate CrCl using the updated Schwartz "bedside" formula (Schwartz et al, 2009).
 - o Collect results of blood cultures only if conducted per standard of care.
 - o Collect purulent material from bone only if a procedure is performed for standard of care.

